15.2 Individually randomized trials in Phase A

For all studies, the community-level inclusion/exclusion criteria, individual-level inclusion/exclusion criteria, recruitment process, study interventions, and study procedures have previously been described. Briefly in each trial, consenting participants will be randomized in a 1:1 ratio to the intervention or standard-of-care. Blocked randomization will be stratified on site and further stratified by sex for certain trials enrolling both sexes. All analyses of Dynamic Prevention in Phase A will restrict to participants enrolled before September 1, 2021.

The primary outcome for the individual-level prevention trials will be biomedical covered time defined as the proportion of follow-up time that the participant is protected from HIV infection with either PrEP or PEP. Follow-up time for the primary outcome will be over 48 weeks; follow-up time will be censored at HIV seroconversion, death, or withdrawal. Secondary and sensitivity analyses will examine alternative definitions of covered time, including restricting follow-up to periods of self-reported HIV risk.

The primary outcome for the individual-level treatment trials is an indicator of viral suppression (HIV RNA<400 cps/mL). The primary outcome is viral suppression at 48 weeks for the mobility intervention trial and 24 weeks for the alcohol intervention trial. In both trials, the primary analysis will exclude individuals who die or withdraw during follow-up; the alcohol intervention study will additionally exclude participants who move out of the study region. In the primary analysis, participants who do not have a viral load measurement within the ascertainment window will be assumed to be un suppressed; secondary analyses will adjust for incomplete ascertainment of viral loads. Additional sensitivity analyses will assess the robustness of these analytic choices.

The primary outcome for the hypertension linkage trial is an indicator of linkage to hypertension care by 30 days. The primary definition will rely on clinical records; individuals without records will be assumed to never have linked. To assess the impact of the voucher, we will

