examine, as a secondary outcome, linkage to the scheduled appointment. **The primary outcome for the hypertension treatment trial is blood pressure control (<140/90 mmHg) at 24 weeks.** The primary definition will rely on three repeated blood pressure measurements using standard procedures, with participants considered controlled if the average of the 2nd and 3rd measurements is <140/90 mmHg. In the primary analysis, participants who do not have their blood pressure measured within the ascertainment window will be assumed to be uncontrolled; secondary analyses will adjust for incomplete ascertainment of blood pressure measures.

In these trials, we will evaluate the interventions using targeted maximum likelihood estimation (TMLE), which provides precision and power gains over an unadjusted approach (e.g., the Student's t-test) by adjusting for stratification factors and for chance imbalance between randomized arms on additional baseline predictors of the outcome.¹⁰⁴ In secondary analyses, we will also implement an unadjusted estimator, the contrast of arm-specific average outcomes. In the prevention trials, we will test the null hypothesis of no changes in covered time due to the intervention with a two-sided test at the 5% significance level. In the treatment and linkage trials, we will test the null hypothesis of no improvements in outcomes due to the intervention with a one-sided test at the 5% significance level. We will also report point estimates and 95% confidence intervals for each effect measure and the arm-specific average outcomes.

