The intervention is delivered by a mobility coordinator, stationed at each clinic, and follow-up is over 48 weeks.

The primary objective is to evaluate if the intervention improved viral suppression (<400 copies/mL) among mobile PWH at week-48. Secondary endpoints, compared

between randomized arms, include retention in HIV care and ART possession. Additionally, within the intervention arm, we will report coverage and uptake of the intervention components at both scheduled and unscheduled visits.

2. Population and Characteristics

The population of interest is PWH who are aged 15+ years, enrolled or new to HIV care, at risk of viral non-suppression (HIV RNA>400 copies/mL in the past year or 2+ missed HIV care visits in the past year), and mobile (2+ weeks out of the community in the past year).

To characterize measurement of this population, we will provide a participant flow diagram (i.e., a CONSORT diagram). Overall and stratified by trial arm and further by sex, we will summarize the baseline characteristics, including sex, age, country, marital status, occupation, education level, alcohol use (any use in past 3 months), mobility metrics (nights away in past 3 months and in past 12 months), impact of mobility on HIV care (missed visits and missed ART doses), baseline ART status and regimen, baseline viral suppression status, and trial enrollment criteria. We will categorize age as “younger” if aged 15-30 years and define persons to be “highly mobile” if they report spending >14 nights away from the community in the past 3 months.

3. Endpoint Measurement and Definition

The **primary endpoint** is HIV viral suppression (HIV RNA<400 copies/mL) at 48-weeks. The primary analytic population consists of all living study participants who have not transferred HIV care to another health facility (as documented in clinical records). In other words, the primary analysis will exclude persons who died, withdrew, or transferred care, but will, otherwise, include persons regardless of their level of mobility or history of movement in/out of the community. In the primary analysis, missing endpoint viral loads will be treated as failures (i.e., unsuppressed). In pre-specified sensitivity analyses, described below, we will assess the robustness of these analytic choices.

Based on review of Ministry of Health medical and pharmacy records, we will also examine the following **secondary endpoints**:

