- Retention in care: the proportion of follow-up time where the participant is engaged in clinical care
- ART possession: the proportion of follow-up time where the participant has a full regimen of ART

We will calculate total follow-up time for each participant as the number of days from their trial enrollment to their week-48 viral load measure. (For persons without a week-48 viral load measure, we will use the close the endpoint ascertainment window.) Out-of-care time will start 14 days after a missed visit and end at re-engagement in care.

4. Evaluation of the SEARCH Intervention Effect

We will assess the intervention effect with targeted minimum loss-based estimation (TMLE), which improves precision and power by adaptively adjusting for baseline outcome predictors.^{1–5} Here, we will use **TMLE with Adaptive Pre-specification** to flexibly control for baseline covariates, while maintaining Type-I error control and accounting for the randomization scheme.^{6–8} Using 10-fold cross-validation, we will choose the optimal approach for estimating the outcome regression (i.e., the expected outcome given the randomization arm and adjustment covariates) and the known propensity score (i.e., the conditional probability of being randomized to the intervention given the adjustment covariates). Specifically, we will select the combination of estimators (adjustment variables + approach) that minimizes the cross-validated variance estimate.

Our pre-specified, candidate adjustment variables consist of sex, age, country, being new to care at enrollment, baseline mobility (number of nights away from the community in the past 12 months), baseline viral suppression status, and nothing (i.e., unadjusted). Our pre-specified, candidate learners consist of generalized linear models (GLMs) adjusting for a single variable beyond the intervention indicator, stepwise regression, multivariate adaptive regression splines (MARS), MARS after screening based on outcome correlations, and the arm-specific mean outcome.

Primary effect estimates will be for the study sample and on the **ratio scale**:

$1/n \sum_{i=1}^n Y_i(1) \div 1/n \sum_{i=1}^n Y_i(0)$, where $Y_i(1)$ denotes the counterfactual outcome for participant i under the intervention and $Y_i(0)$ denotes the counterfactual outcome for participant i under the control.^{9–11} Secondary comparisons will be on the difference scale.

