The **primary endpoint** is HIV viral suppression (HIV RNA<400 copies/mL) at 24-weeks. The primary analytic population will consist of all study participants residing in the study region. In other words, the primary analysis will exclude persons who died, withdrew, or moved out of the study region. In the primary analysis, missing endpoint viral loads will be treated as failures (i.e., un suppressed). In pre-specified sensitivity analyses, described below, we will assess the robustness of these analytic choices.

We will also examine the following **secondary endpoints** to capture alcohol use at 24-weeks:

- Composite measure of unhealthy alcohol use: AUDIT-C ≥ 3 for women and ≥ 4 for men or PEth ≥ 50 ng/mL
- AUDIT-C ≥ 3 for women and ≥ 4 for men
- PEth ≥ 50 ng/mL
- Composite measure of unhealthy alcohol use: AUDIT-C ≥ 6 or PEth > 200 ng/mL
- AUDIT-C ≥ 6
- PEth > 200 ng/mL
- Log-10 transformed PEth (treated continuously)

Pending data availability, we will define the primary and secondary endpoints analogously at 48-weeks.

4. Evaluation of the SEARCH Intervention Effect

We will assess the intervention effect with targeted minimum loss-based estimation (TMLE), which improves precision and power by adaptively adjusting for baseline outcome predictors.^{1–5} Here, we will use **TMLE with Adaptive Pre-specification** to flexibly control for baseline covariates, while maintaining Type-I error control and accounting for the randomization scheme.^{6–8} Using 10-fold cross-validation, we will choose the optimal approach for estimating the outcome regression (i.e., the expected outcome given the randomization arm and adjustment covariates) and the known propensity score (i.e., the conditional probability of being randomized to the intervention given the adjustment covariates). Specifically, we will select the combination of estimators (adjustment variables + approach) that minimizes the cross-validated variance estimate.

Our pre-specified, candidate adjustment variables consist of sex, age, country, baseline viral suppression status, baseline PEth (log-10 transformed), baseline AUDIT-C score, and nothing (i.e., unadjusted). Our pre-specified, candidate learners consist of generalized linear models (GLMs) adjusting for a single variable beyond the intervention indicator, stepwise regression, multivariate adaptive regression splines (MARS), MARS after screening based on outcome correlations, and the arm-specific mean outcome.

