In Phase A of SEARCH-Sapphire (NCT04810650), we are conducting an individually randomized controlled trial to evaluate the effect of Dynamic Choice HIV Prevention (DCP) delivered at Outpatient Departments on biomedical HIV prevention coverage in rural Kenya and Uganda. Details of the trial design and procedures can be found in the corresponding Study Protocol. Analyses plans for qualitative outcomes and cost-effectiveness outcomes are available elsewhere. Power calculations are given in the Appendix.

In brief, from April-July 2021, we enrolled 403 participants who were currently or anticipated being at risk of HIV. These participants were randomized to the DCP intervention or the standard-of-care using a stratified random block design with stratification factors of country and sex and with random block sizes of 2 and 4. The randomization list was generated by an independent researcher.

The DCP intervention includes choice of HIV prevention product (oral pre-exposure prophylaxis [PrEP] or post-exposure prophylaxis [PEP]), choice in HIV testing, choice in service location, and provider training on patient-centered care. Follow-up is over 48 weeks.

The primary objective is to evaluate if the DCP intervention improved biomedical HIV prevention coverage, defined as the proportion of the follow-up where the participant self-reported using PrEP or PEP. Secondary endpoints include biomedical covered time during periods of self-assessed HIV risk (compared between randomized arms) as well as coverage and uptake of the DCP intervention components (within intervention arm only).

2. Population and Characteristics

The population of interest is persons aged 15+ years who are seen at Outpatient Departments and report current or anticipated HIV risk, as assessed via the country-specific Ministry of Health screening tools or self-assessed.

To characterize measurement of this population, we will provide a participant flow diagram (i.e., a CONSORT diagram). Overall and stratified by trial arm and further by sex, we will summarize the baseline characteristics, including sex, age, country, marital status, occupation, HIV risk criteria, alcohol use (any in prior 3 months), mobility (nights away in the past 3 months), pregnancy (women only), circumcision (men only), and any prior use of PrEP or PEP in the past 6 months. We will categorize age in “younger” if aged 15-24 years.

3. Endpoint Measurement and Definition

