Our pre-specified, candidate adjustment variables consist of sex, age, country, use of PrEP/PEP before enrollment, and nothing (i.e., unadjusted). Our pre-specified, candidate learners consist of generalized linear models (GLMs) adjusting for a single variable (beyond the intervention indicator), stepwise regression, multivariate adaptive regression splines (MARS), and the arm-specific mean outcome.

Primary effect estimates will be for the study sample and on the **difference scale**: $1/n \sum_{i=1}^n [Y_i(1) - Y_i(0)]$, where $Y_i(1)$ denotes the counterfactual outcome for participant i under the intervention and $Y_i(0)$ denotes the counterfactual outcome for participant i under the control.^{9–11} Secondary comparisons will be on the ratio scale.

We will test the **null hypothesis** that the intervention did not change biomedical covered time with a two-sided test at the 5% significance level. We will also report point estimates and 95% confidence intervals for each effect measure and the arm-specific outcomes. Standard error estimation will be based on the estimated influence curve, and statistical inference will follow from the Central Limit Theorem (i.e., using the standard normal distribution).¹

Secondary analyses: To assess the robustness of these findings, we will repeat these analyses using the unadjusted effect estimator. We will also repeat these analyses using TMLE to adjust for missing endpoints.

Subgroup analyses: We will repeat these analyses within strata defined by country, sex, age group, alcohol use, and use of PrEP/PEP in the 6 months before enrollment. In subgroups with fewer than 41 participants, we will limit the candidate estimation approaches to main terms adjustment for a single covariate or the simple mean and use

leave-one-out cross-validation. To further understand effect heterogeneity, we may conduct variable importance measures (i.e., unadjusted and adjusted predictor analyses) with TMLE.

Secondary endpoints compared by arm: We will implement analogous analyses to evaluate the intervention effect on biomedical covered time at-risk, possession covered time (overall and at-risk), and use/possession ratio (overall and at-risk).

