- Use/possession ratio, defined as the proportion of follow-up with PrEP or PEP pills where the participant reports taking them
- Use/possession ratio when at-risk

4. Evaluation of the SEARCH DCP Intervention Effect

We will assess the Dynamic Choice Prevention intervention effect with targeted minimum loss-based estimation (TMLE), which improves precision and power by adaptively adjusting for baseline outcome predictors.^{1–5} Here, we will use **TMLE with Adaptive Pre-specification** to flexibly control for baseline covariates, while maintaining Type-I error control and accounting for the randomization scheme.^{6–8} Using 10-fold cross-validation, we will chose the optimal approach for estimating the outcome regression (i.e., the expected outcome given the randomization arm and adjustment covariates) and the known propensity score (i.e., the conditional probability of being randomized to the intervention given the adjustment covariates). Specifically, we will select the combination of estimators (adjustment variables + approach) that minimizes the cross-validated variance estimate.

Our pre-specified, candidate adjustment variables consist of pregnancy status at enrollment, age, country, use of PrEP/PEP in the 6 months before enrollment, and nothing (i.e., unadjusted). Our pre-specified, candidate learners consist of generalized linear models (GLMs) adjusting for a single variable (beyond the intervention indicator), stepwise regression, multivariate adaptive regression splines (MARS), and the arm-specific mean outcome.

Primary effect estimates will be for the study sample and on the **difference scale**: $1/n \sum_{i=1}^n [Y_i(1) - Y_i(0)]$, where $Y_i(1)$ denotes the counterfactual outcome for participant i under the intervention and $Y_i(0)$ denotes the counterfactual outcome for participant i under the control.^{9–11} Secondary comparisons will be on the ratio scale.

We will test the **null hypothesis** that the intervention did not change biomedical covered time with a two-sided test at the 5% significance level. We will also report point estimates and 95% confidence intervals for each effect measure and the arm-specific outcomes. Standard error estimation will be based on the estimated influence curve, and statistical inference will follow from the Central Limit Theorem (i.e., using the standard normal distribution).¹

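### Protocol 15.2 promises randomisation stratified on site and adjustment for the strata, but five of the six individual-trial SAPs record country strata and leave clinic site out of the candidate adjusters; the cost is some precision, not validity

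*SAP*

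**What the plan says.** Protocol 15.2, on the individually randomised Phase A trials: "Blocked randomization will be stratified on site and further stratified by sex for certain trials enrolling both sexes". The same section says that the TMLE gains precision "by adjusting for stratification factors and for chance imbalance between randomized arms on additional baseline predictors of the outcome".

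The SAPs record something else:

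| SAP | Strata recorded | Candidate adjusters, apart from none |
|---|---|---|
| Outpatient | country, sex | sex, age, country, prior PrEP/PEP use |
| Antenatal | country, pregnancy status | pregnancy status, age, country, prior PrEP/PEP use |
| Mobility | country, sex | sex, age, country, new to care, baseline mobility, baseline suppression |
| Alcohol | country, sex | sex, age, country, baseline suppression, PEth, AUDIT-C |
| Severe hypertension | country, sex | age, sex, baseline severity, country |
| Hypertension linkage | not stated | age, sex, severity, **site** |

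The outpatient, mobility and alcohol overviews use the same words for the strata: "stratification factors of country and sex and with random block sizes of 2 and 4". The outpatient list of adjusters (section 4) is "Our pre-specified, candidate adjustment variables consist of sex, age, country, use of PrEP/PEP before enrollment, and nothing (i.e., unadjusted". The antenatal, mobility and alcohol lists open with "candidate adjustment variables consist of pregnancy status at enrollment, age, country, use of PrEP/PEP in the 6 months before enrollment", "candidate adjustment variables consist of sex, age, country, being new to care at enrollment, baseline mobility" and "candidate adjustment variables consist of sex, age, country, baseline viral suppression status, baseline PEth (log-10 transformed), baseline AUDIT-C score". The alcohol SAP does mention a trial recruitment site, but that separates venue-based from clinic recruitment; it is a subgroup variable and not an adjuster.

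**The concern.** The two accounts of the strata cannot both be right, and the strata bear on how the standard error should be computed and on how the trials are reported. Under either account, the five analyses cannot adjust for clinic.

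Clinic is a plausible predictor of outcome here, because delivery is local. In the mobility trial, "The intervention is delivered by a mobility coordinator, stationed at each clinic". In the prevention trials, Protocol 9.2.1.4 gives participants one clinician's phone number at each facility, and control care comes from local government services.

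Country does not identify clinic. Protocol Appendix 18 lists two outpatient and two antenatal facilities in each country. The severe-hypertension trial ran in three communities across two countries, so one country holds two of them.

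At stake is precision, and in one case a standard error that is a little too wide.

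**Working it through.** **The plan's own figure.** Protocol 15.2.1 gives 200 per arm, SD 0.35, a two-sided 5% test and 80% power at 9.8 points for the outpatient and antenatal trials. SE = 0.35 × √(2/200) = 0.035, and 0.098/0.035 = 2.80. The t-test calculation gives a detectable effect of 9.83 points and 79.8% power at 9.8 points, so the figure reproduces. (The two SAP appendices assume an SD of 0.3; that is a separate matter, and the protocol value is used here.)

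**Outpatient and antenatal trials, with clinic adjustment.** Let r be the share of outcome variance due to clinic differences within country. The documents give no value, so r is an assumption. The residual SD after adjustment is 0.35 × √(1 − r). With two equal clinics per country, r corresponds to clinics lying ±0.35 × √r around the country mean.

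| r | Clinics around country mean | Residual SD | Detectable effect | Power at 9.8 points |
|---|---|---|---|---|
| 0 | 0 | 0.350 | 9.83 | 79.8% |
| 2% | ±4.9 points | 0.346 | 9.73 | 80.6% |
| 5% | ±7.8 points | 0.341 | 9.58 | 81.7% |
| 10% | ±11.1 points | 0.332 | 9.32 | 83.8% |

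**Does the omission threaten validity?** A simulation used 400 participants in four clinics of 100, two per country, a constant effect of 9.8 points and 3,000 replicates. It compared linear models adjusted for country with models adjusted for clinic.

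- *Allocation within country.* Estimates were unbiased (0.097 to 0.100 against 0.098) and coverage was about 94% to 96%. Power with country adjustment was about 80%, against 81% to 84% with clinic adjustment, for r from 2% to 10%. Clinic mix can differ between arms by chance. For a clinic of 100 in a country of 200 split equally, the SD of its intervention count is √(100 × 0.5 × 0.5 × 100/199) = 3.5, a 95% range of 43 to 57. The standard error already carries that variation.
- *Allocation within clinic.* The design already balances clinics, so the estimate itself loses nothing. At r = 10% the country-adjusted standard error averaged 0.0350 against an empirical 0.0335. The test is then slightly conservative.

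Because the simulated effect is a constant shift, coverage of about 94% to 96% also means a two-sided error rate near 5%.

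**Binary-outcome trials.** For mobility, alcohol and severe hypertension, Protocol 15.2.1 assumes 40% in control. The variance is 0.4 × 0.6 = 0.24. For two equal clinics lying ±d around the country mean, the SE ratio is √(1 − d²/0.24).

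| d | SE ratio | SE cut | Equivalent sample size |
|---|---|---|---|
| 5 points | √(1 − 0.0025/0.24) = 0.995 | 0.5% | 1.01 × |
| 10 points | √(1 − 0.0100/0.24) = 0.979 | 2% | 1.04 × |
| 15 points | √(1 − 0.0225/0.24) = 0.952 | 5% | 1.10 × |

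The last row means a 30-point gap between two clinics in one country, which nothing in the documents supports. The number of clinics is not stated for the mobility or alcohol trial, so these rows are illustrations there. For severe hypertension they can apply only in the country with two communities.

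**The case against.** The best defence is that this is a documentation slip of little consequence. The SAPs describe randomisation already done and may simply be the accurate record. Sample sizes came from unadjusted tests, and the appendices treat covariate adjustment as a bonus, so no planned power is lost. Prior PrEP/PEP use, baseline suppression and PEth are also candidates and may absorb part of any clinic difference. Effects of staff who serve only the intervention arm would need arm-by-clinic terms to remove fully. Finally, Adaptive Pre-specification depends on fixing the candidates in advance. Enrolment in the outpatient, antenatal and mobility trials ended in July 2021 with 48 weeks of follow-up, so a late addition could be a post hoc change to the primary estimator.

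Most of this stands, and it limits the point to precision and consistency. It does not remove the contradiction. Nor can site in Protocol 15.2 easily be read as country: the linkage SAP lists the two as separate subgroup variables. No SAP explains why site is a candidate in the linkage trial but not in the severe-hypertension trial, which also ran in three communities.

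A reader might go further and infer that the effect estimates are biased, that the tests are anti-conservative, or that all differences between sites stay in the error. The documents do not support this. Randomisation is individual, the calculations show no bias or inflated error rate, and country is a candidate in all five SAPs.

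**Conclusion.** The mismatch is plain on the text, and five of the six individual-trial SAPs cannot adjust for clinic. The consequence is modest. If allocation was by country, some precision is given up; if it was by site, the reported standard error is slightly too large.

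In the outpatient and antenatal trials the gain at 9.8 points is 0.8, 1.9 or 4.0 percentage points of power for r of 2%, 5% or 10%. In the binary-outcome trials it is a standard-error cut of about 0.5% to 5%. These figures rest on assumed clinic differences, equal clinic sizes, site being selected, and the other candidates explaining none of the clinic difference.

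A reader might also conclude that the five SAPs owe a subgroup analysis by site because the linkage SAP has one. They do not: Protocol 15.4 names country, sex, age group and possibly mobility. The change is worth making because it costs almost nothing, and the strata must be stated correctly whatever the size of the gain.

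**What to change.** 1. Add clinic site to the candidate adjustment variables, for both the outcome regression and the propensity score, in the outpatient, antenatal, mobility, alcohol and severe-hypertension SAPs, as the linkage SAP already does. Do this only where outcomes have not yet been analysed by arm. Where they have, keep the existing primary analysis and report site adjustment as a labelled sensitivity analysis.
2. Check the randomisation lists, then correct Protocol 15.2 or the SAPs so that both state the strata actually used and whether the analysis adjusts for them.

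The cost is a wording change. The clinic of enrolment should be known for every participant, cross-validation keeps site only if it lowers the estimated variance, and a few extra terms matter little in samples of 200 to about 400.
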